10 ADVERSE EXPERIENCE REPORTING AND DOCUMENTATION

10.1 Adverse Events

An adverse event (AE) is any untoward medical occurrence in a clinical investigation of a patient administered a pharmaceutical product and that does not necessarily have a causal relationship with the treatment. An AE is therefore any unfavorable and unintended sign (including an abnormal laboratory finding), symptom or disease temporally associated with the administration of an investigational product, whether or not related to that investigational product. An unexpected AE is one of a type not identified in nature, severity, or frequency in the current Investigator's Brochure or of greater severity or frequency than expected based on the information in the Investigator's Brochure.

The Investigator will probe, via discussion with the participant, for the occurrence of AEs during each participant visit and record the information in the site's source documents. Adverse events will be recorded in the patient CRF. Adverse events will be described by duration (start and stop dates and times), severity, outcome, treatment and relation to study drug, or if unrelated, the cause.

AE Severity

The National Cancer Institute's Common Terminology Criteria for Adverse Events (CTCAE) Version 3.0 should be used to assess and grade AE severity, including laboratory abnormalities judged to be clinically significant. The modified criteria can be found in the study manual. If the experience is not covered in the modified criteria, the guidelines shown in Table 1 below should be used to grade severity. It should be pointed out that the term "severe" is a measure of intensity and that a severe AE is not necessarily serious.

Table 1. AE Severity Grading

Severity (Toxicity Grade)	Description
Mild (1)	Transient or mild discomfort; no limitation in activity; no medical intervention or therapy required. The participant may be aware of the sign or symptom but tolerates it reasonably well.
Moderate (2)	Mild to moderate limitation in activity, no or minimal medical intervention/therapy required.
Severe (3)	Marked limitation in activity, medical intervention/therapy required, hospitalizations possible.
Life-threatening (4)	The participant is at risk of death due to the adverse experience as it occurred. This does not refer to an experience that hypothetically might have caused death if it were more severe.

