10.3 Monitoring

During the study, safety will be monitored by a Safety Monitoring Committee (SMC), which will be led by a qualified UCSF faculty member in the Department of Medicine with expertise in HIV clinical research (see Section 13 below). The SMC will review all study procedures before the initiation of the study. They will have the full and final authority to stop the study for any safety concern at any point. The Principal Investigator will be the primary medical monitor responsible for study adverse event monitoring and will report adverse events and unanticipated problems to the UCSF IRB and the SMC. All participants will be followed for possible adverse events and unanticipated problems throughout the study period.

Participants will be monitored in an outpatient clinic during the first 6 hours post-dose on dosing days. At each visit, participants will be assessed for any new symptoms, and a study coordinator will obtain vital signs. The study will require 48-hour reporting of all laboratory values, signs/symptoms, and serious adverse events (SAEs). The study will have intensive Phase I safety monitoring, which will include regular and frequent team review (every week for the first 2 months of the study; then every two weeks thereafter) of all reported events. In addition, for any Grade 3 or 4 events, sites will be instructed to contact the study team by email.

- Grade 1 or 2 Toxicity: Participants who develop a Grade 1 or 2 AE or toxicity may continue study treatment. If a participant chooses to discontinue study treatment, the site should notify the study protocol core team as noted above, and encourage the participant to complete any remaining study visits.
- Grade 3 or 4 Toxicity: Participants experiencing Grade 3 or 4 AEs requiring permanent discontinuation of study treatment should be followed closely for resolution of the AE to Grade ≤ 3 and the protocol core team must be notified. Participants discontinuing study treatment should be encouraged to complete any remaining study visits.

[name] will be contacted directly to report medical concerns or questions regarding safety.

[contact]

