10.4 Criteria for Discontinuation

Safety will be monitored by the dedicated SMC, led by a qualified Drug and Substance Abuse specialist in the UCSF Department of Medicine (see Section 13 below). The SMC will have full and final authority to stop the study at any point for safety concerns. The decision to proceed with further drug administration will be taken by the Principal Investigator, taking into consideration clinical and laboratory adverse events. The decision to proceed with the next dosing level will be taken by the SMC. Specifically,

dosing will be paused and the SMC will be consulted if one Grade 4 or two Grade 3 drug related adverse events or laboratory abnormalities are reported.

Specifically, safety discontinuation criteria will include:

1. Any serious adverse event assessed as at least possibly related to study treatment:
 - a. Any Grade 4 drug-related adverse event or laboratory abnormality
 - b. Two Grade 3 drug-related adverse event or laboratory abnormality
2. Pregnancy or breastfeeding
3. Requirement for prohibited concomitant medications (see section 7.1)
4. Clinical reasons believed life threatening by the physician, even if not addressed in the toxicity section of the protocol

Study drug-specific hold criteria after the first methamphetamine dose will be based on established protocols adapted from prior stimulant interventional trials (Walsh et. al.

Drug Alcohol Depend. 2010 Jan 1;106(1):28-37. doi: 10.1016/j.drugalcdep.2009.07.011):

- SBP \geq 165 mm Hg or
- DBP \geq 100 mm Hg or
- HR \geq 130 BPM

Resume methamphetamine administration only if values are below the above parameters for at least 3 consecutive minutes.

Stop further methamphetamine administration if the following are reached for 4 minutes or more:

- SBP \geq 180 mm Hg or
- DBP \geq 120 mm Hg or
- HR \geq submaximal HR (i.e., 220 - [age x 0.85])

Such a participant will be observed until cardiac parameters return to normal and will be discontinued from the study.

In addition, any significant ECG abnormality (determined by monitoring medical staff) will suspend further dosing.

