11 DISCONTINUATION AND REPLACEMENT OF PARTICIPANTS

11.1 Early Discontinuation of Study Drug

A participant may be discontinued from study treatment at any time if the participant or the investigator feels that it is not in the participant's best interest to continue. The following is a list of possible reasons for study treatment discontinuation:

- Participant withdrawal of consent
- Participant is not compliant with study procedures
- Adverse event that in the opinion of the investigator would be in the best interest of the participant to discontinue study treatment
- Protocol violation requiring discontinuation of study treatment
- Lost to follow-up
- Sponsor request for early termination of study
- Positive pregnancy test or breastfeeding (females)

If a participant is withdrawn from treatment due to an adverse event, the participant will be followed and treated by the Investigator until the abnormal parameter or symptom has resolved or stabilized.

All participants who discontinue study treatment should come in for an early discontinuation visit as soon as possible and then should be encouraged to complete all remaining scheduled visits and procedures.

All participants are free to withdraw from participation at any time, for any reason, specified or unspecified, and without prejudice.

Reasonable attempts will be made by the investigator to provide a reason for participant withdrawals. The reason for the participant's withdrawal from the study will be specified in the participant's source documents (refer to early termination procedures).

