12.4 Replacement of Participants

Participants who withdraw from the study treatment before last day of study drug dosing will be replaced by another enrolled participant to maintain total study numbers.

The CRF will document the reason for the withdrawal and date of withdrawal. Date of withdrawal will be documented as the date of last study drug treatment, not the date that the decision to withdraw treatment was made.

Participants will be followed after withdrawal from the study for 3 calendar days after cessation of treatment. All adverse events during that period will be reported.

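### The Section 10.3 follow-up endpoint for Grade 3 or 4 events asks for no improvement from a Grade 3 event, and it is not reconciled with Sections 11.1, 10.4 and 12.4

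*Combined protocol and SAP*

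**What the plan says.** Section 10.3 (Monitoring) divides toxicity management by grade. For the upper two grades its scope is limited: "Participants experiencing Grade 3 or 4 AEs requiring permanent discontinuation of study treatment should be followed closely for resolution of the AE to Grade". The endpoint is that they be "followed closely for resolution of the AE to Grade ≤ 3 and the protocol core team must be notified". The same section also contains a general commitment: "All participants will be followed for possible adverse events and unanticipated problems throughout the study period".

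Section 10.1, Table 1, is the scale for events that the modified CTCAE criteria do not cover. It describes Grade 3 (severe) as "Marked limitation in activity, medical intervention/therapy required, hospitalizations possible".

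Three other sections set follow-up rules that can apply to the same people:

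- Section 11.1, for a participant taken off treatment because of an adverse event: "the participant will be followed and treated by the Investigator until the abnormal parameter or symptom has resolved or stabilized".
- Section 10.4, for a participant who reaches the blood pressure or heart rate stop thresholds for 4 minutes or more: "Such a participant will be observed until cardiac parameters return to normal and will be discontinued from the study".
- Section 12.4 (Replacement of Participants): "Participants will be followed after withdrawal from the study for 3 calendar days after cessation of treatment". It adds that adverse events in that period are to be reported.

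**The concern.** A follow-up endpoint should describe a state that the triggering event has not yet reached. The one in Section 10.3 includes one of its own two triggers. It is also the only one of the four rules written by toxicity grade, so a site looking for the rule on a Grade 3 or 4 event would naturally turn to it first.

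What is at stake is clarity about how long a participant with a severe, treatment-ending event is followed, and under which rule. Incidence and nature of adverse events is the trial's safety evaluation (Section 5.2). Participants are treated as non-tolerant to the stimulant (Section 8.3.1). With only 10 participants planned, each severe event carries weight in what the SMC reviews.

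**Working it through.** No sample size, power or alpha figure bears on this point, so there is no plan figure to reproduce. The check is one of logic, followed by a side-by-side reading.

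**Step 1: test the 10.3 criterion against its two triggers.**

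- Grade 3 at onset: 3 ≤ 3 is true. The endpoint is met at once and no improvement is required.
- Grade 4 at onset: 4 ≤ 3 is false. The endpoint is met after a fall of one grade (4 − 1 = 3), while the event is still severe on Table 1.

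The criterion therefore separates Grade 4 from everything else and is empty for Grade 3. This holds on whichever grading scale is used. Only the description of Grade 3 as severe rests on Table 1.

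**Step 2: set the four rules side by side.**

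| Section | Who it covers | Endpoint | Already met by a Grade 3 event at onset? |
|---|---|---|---|
| 10.3 | Grade 3 or 4 event that ends treatment permanently | Grade ≤ 3 | Yes |
| 11.1 | Withdrawn from treatment because of an adverse event | Resolved or stabilized | Not by grade alone; no grade is stated |
| 10.4 | Cardiovascular stop threshold reached for 4 minutes or more | Cardiac parameters normal | No |
| 12.4 | Withdrawn from the study | 3 calendar days after treatment ends | Not applicable; a fixed period |

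**Step 3: look for one participant under several rules.** Suppose systolic pressure is at or above 180 mmHg on the lowest repeat reading of the visit, without the Grade 4 features. The Section 10.1 table grades this as Grade 3. If the value also holds for 4 minutes or more, Section 10.4 stops dosing, requires observation to normal and discontinues the participant from the study. Discontinuation from the study brings in the 3-day period of 12.4. Stopping treatment because of the event brings in 11.1. The endpoint in 10.3 was met when the event was graded. One person then has four rules with four endpoints.

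**Step 4: ask whether Section 10.4 covers the gap.** It does so only in part.

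- A diastolic pressure of 110 to 119 mmHg is Grade 3 in the Section 10.1 table (110 or above) but lies below the 10.4 diastolic stop threshold of 120.
- A QTc above 0.50 seconds is also Grade 3. For a significant ECG abnormality, however, 10.4 says only that dosing is suspended and gives no follow-up endpoint.

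If such an event led to permanent discontinuation, the return-to-normal rule would not reach it unless another stop threshold was also met. Sections 10.3 and 11.1 would remain.

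**Step 5: ask whether Section 11.1 covers the gap.** Largely it does, because it requires follow-up and treatment for anyone withdrawn from treatment because of an adverse event. Its stabilization limb names no grade, however, so an event that is stable at Grade 3 could satisfy both 11.1 and 10.3.

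**The case against.** The strongest reply is that Section 10.3 does not stand alone. Section 11.1 covers the same participants and is mandatory in tone. Section 10.3 itself follows everyone for adverse events through the study period and encourages those who stop treatment to finish their visits. Serious events are collected to the final visit (Section 10.2.1). The rules can also be met together: a site that follows a participant under 11.1 has satisfied 10.3 as well. All of this stands, and it limits the point to an ineffective criterion and an unresolved inconsistency.

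A reader might infer more than that. Four stronger readings are not supported:

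- **That required follow-up of severe toxicity can end as soon as it begins.** Only the 10.3 criterion is exhausted at onset. Section 11.1 continues to apply.
- **That every Grade 3 event is affected.** The sentence is limited to events that end treatment permanently, and treatment is one day per arm.
- **That a single systolic reading of, say, 185 mmHg would close follow-up.** The table grades on the lowest reading after repeat testing, and the 10.4 stop needs 4 minutes or more. Where both conditions are met, 10.4 requires observation until normal.
- **That adverse event records or SMC summaries would be cut short.** Section 9.1.7 requires start and stop dates, grade and outcome without reference to the 10.3 endpoint. Nothing says that data capture ends when that endpoint is reached.

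The reply does not repair the text of 10.3 or state an order of precedence. Collection of serious events is not a full backstop either, since Section 10.1 notes that a severe event need not be a serious one.

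**Conclusion.** The point holds in a limited form. As written, the 10.3 endpoint requires no improvement for one of the two grades it covers, and only a one-grade fall for the other. It is inconsistent with up to three other rules that can apply to the same participant, and the documents do not say which governs.

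The practical size is modest. The sentence applies only to Grade 3 or 4 events that end treatment permanently, among 10 planned participants. Section 11.1 already requires substantive follow-up for them. No analysis, estimate or power figure changes. It should be corrected because it is a stated safety criterion that does not work as worded, but it does not by itself undermine the trial.

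The conclusion assumes that the symbol and grade are as printed. The documents cannot show whether they are a drafting slip, and the wording is ineffective either way. It also assumes that the study manual, which holds the modified grading criteria and is not among the documents, does not settle precedence.

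**What to change.** Reconcile Section 10.3 with Sections 11.1, 10.4 and 12.4 in one amendment that does two things:

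1. Restates the 10.3 endpoint as a state that neither a Grade 3 nor a Grade 4 event already meets at onset.
2. Says which rule applies to whom: a participant who stops treatment but stays in the study, one stopped on the cardiovascular thresholds, and one withdrawn from the study. It should say in particular whether the 3-day period in 12.4 is a minimum or a limit when an event is still open.

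The choice of endpoint belongs to the sponsor and the SMC; no grade or clinical rule is proposed here. The sections need not share identical wording so long as they do not conflict.

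The cost is a short text amendment with the IRB approval that Section 16.1 requires, and little or no follow-up beyond what 11.1 already asks for.

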10.4 Criteria for Discontinuation

Safety will be monitored by the dedicated SMC, led by a qualified Drug and Substance Abuse specialist in the UCSF Department of Medicine (see Section 13 below). The SMC will have full and final authority to stop the study at any point for safety concerns. The decision to proceed with further drug administration will be taken by the Principal Investigator, taking into consideration clinical and laboratory adverse events. The decision to proceed with the next dosing level will be taken by the SMC. Specifically,

dosing will be paused and the SMC will be consulted if one Grade 4 or two Grade 3 drug related adverse events or laboratory abnormalities are reported.

Specifically, safety discontinuation criteria will include:

1. Any serious adverse event assessed as at least possibly related to study treatment:
 - a. Any Grade 4 drug-related adverse event or laboratory abnormality
 - b. Two Grade 3 drug-related adverse event or laboratory abnormality
2. Pregnancy or breastfeeding
3. Requirement for prohibited concomitant medications (see section 7.1)
4. Clinical reasons believed life threatening by the physician, even if not addressed in the toxicity section of the protocol

Study drug-specific hold criteria after the first methamphetamine dose will be based on established protocols adapted from prior stimulant interventional trials (Walsh et. al.

Drug Alcohol Depend. 2010 Jan 1;106(1):28-37. doi: 10.1016/j.drugalcdep.2009.07.011):

- SBP \geq 165 mm Hg or
- DBP \geq 100 mm Hg or
- HR \geq 130 BPM

Resume methamphetamine administration only if values are below the above parameters for at least 3 consecutive minutes.

Stop further methamphetamine administration if the following are reached for 4 minutes or more:

- SBP \geq 180 mm Hg or
- DBP \geq 120 mm Hg or
- HR \geq submaximal HR (i.e., 220 - [age x 0.85])

Such a participant will be observed until cardiac parameters return to normal and will be discontinued from the study.

In addition, any significant ECG abnormality (determined by monitoring medical staff) will suspend further dosing.

If stopping/pausing criteria are not met, the remainder of the dosing cohort will be enrolled/dosed the subsequent week. The study will proceed to the next dosing level provided the stopping/pausing criteria are not met. A UCSF Department of Medicine faculty member who is not otherwise involved in the study and who will not communicate with the study investigators regarding any aspect of the SMC reports will prepare the monitoring reports. The SMC will review accrual, adverse events summaries, CD4+ T-cell counts and HIV RNA levels/suppression over time, off-study rates and completeness of follow-up, by dose cohort.

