EFFICACY EVALUATIONS	
 • HIV virus replication • Immune activation (cell surface immune marker expression by flow cytometry) • Inflammation (plasma cytokine levels) • Gene expression changes (RNA-seq) • Trace amine receptor 1 (TAAR1) signaling
PRIMARY ENDPOINT	
 • HIV virus replication
SECONDARY ENDPOINTS	
 • Immunologic effect on inflammation (immune marker expression, plasma cytokine expression). • Gene expression changes • Trace amine receptor 1 (TAAR1) metabolite production
OTHER EVALUATIONS	
SAFETY EVALUATIONS	Incidence of adverse events
PLANNED INTERIM ANALYSES	
During the study, safety will be monitored by a Safety Monitoring Committee (SMC), which will be led by an HIV specialist. The SMC will review all study procedures before the initiation of the study. They will have the full and final authority to stop the study for any safety concern at any point. The decision to proceed with further drug administration will be taken by the Principal Investigator, taking into consideration clinical and laboratory adverse events. The decision to proceed with the next dosing level will be taken by the SMC. Specifically, dosing will be stopped and the SMC will be notified if one Grade 4 or two Grade 3 drug related adverse events or laboratory abnormalities are reported, becomes pregnant or initiates

	
breastfeeding, or is required to initiate one of the prohibited concomitant medications listed in section 7.1. If stopping/pausing criteria are not met, the remainder of the dosing cohort will be enrolled/dosed the subsequent week. The study will proceed to the next dosing level provided the stopping/pausing criteria are not met. A UCSF Department of Medicine faculty member who is not otherwise involved in the study and who will not communicate with the study investigators regarding any aspect of the SMC reports will prepare the monitoring reports. The SMC will review accrual, adverse events summaries, CD4+ T-cell counts and HIV RNA levels/suppression over time, off-study rates and completeness of follow-up, by dose cohort.

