Grade 1 or 2 AEs will not result in any change to the study plans. If there is evidence for a Grade 3 AE that is not caused by the study drug, the study will continue as planned. On the other hand, Grade 3 AEs thought to be possibly caused by the intervention and any Grade 4 AEs will result in a hold on any future enrollments until a decision to proceed or to stop the study is made by the SMC

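### The Grade 3/4 safety triggers differ between the synopsis, Section 10.4 and Section 13; the label on the 10.4 heart-rate stop also needs checking against its formula

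*Combined protocol and SAP*

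**What the plan says.** Grade 3 and Grade 4 events are dealt with in three places.

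- **Synopsis, Planned Interim Analyses:** "dosing will be stopped and the SMC will be notified if one Grade 4 or two Grade 3 drug related adverse events". Abnormal laboratory findings of the same grades count too.
- **Section 10.4, lead text:** "dosing will be paused and the SMC will be consulted if one Grade 4 or two Grade 3 drug related adverse events". Here too laboratory findings count. The trigger is the same as in the synopsis; the action is not.
- **Section 10.4, numbered list:** the grade criteria appear as sub-items of item 1, which is confined to serious events at least possibly related to treatment. Item 4 adds "Clinical reasons believed life threatening by the physician, even if not addressed in the toxicity section of the protocol".
- **Link to enrolment, in both the synopsis and 10.4:** "If stopping/pausing criteria are not met, the remainder of the dosing cohort will be enrolled/dosed the subsequent week".
- **Section 13:** "Grade 3 AEs thought to be possibly caused by the intervention and any Grade 4 AEs will result in a hold". The hold falls on further enrolment and lasts until the Safety Monitoring Committee (SMC) decides. A Grade 3 event not caused by the drug changes nothing.

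Section 10.4 also sets vital-sign limits after the first methamphetamine dose. One of the permanent stops, if sustained for 4 minutes or more, is a heart rate at or above "submaximal HR (i.e., 220 - [age x 0.85", with the brackets closing straight after the 0.85. The same section has a hold at 130 bpm, blood-pressure holds and blood-pressure stops. It adds that "any significant ECG abnormality (determined by monitoring medical staff) will suspend further dosing" and that "The decision to proceed with further drug administration will be taken by the Principal Investigator".

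**The concern.** A safety rule should give site staff one answer when an event occurs. The three Grade 3/4 statements differ on how many events are needed, whether they must be drug related, what is done, and whether the action falls on dosing or on enrolment. The synopsis and 10.4 start from dosing, but their linking sentence also governs enrolment, which is what Section 13 holds. An event that meets one rule and not the other leaves the site unsure whether the next participant may be enrolled.

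The heart-rate stop raises a smaller question. The brackets apply 0.85 to age alone, and the result is called submaximal. Whether that label fits depends on what the maximal rate is taken to be, and the documents do not say. What turns on it is whether the later capsule on a treatment day (Section 8.4.1) is stopped for good and the participant leaves the study.

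**Working it through.** **Part 1: Grade 3/4 triggers.** Inputs: the synopsis, Section 10.4 and Section 13. I read drug related as at least possibly related, take Section 13 at its natural reading (one possibly related Grade 3 event suffices), and assume that 10.4 item 4 is not met. The Grade 3 rows concern non-serious events.

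| Event | Synopsis and 10.4 trigger met? | Section 13 hold met? | Agree? |
|---|---|---|---|
| Grade 3, related, one | No | Yes | No |
| Grade 3, related, two | Yes | Yes | Yes |
| Grade 3, unrelated, one | No | No | Yes |
| Grade 3, unrelated, two | No | No | Yes |
| Grade 4, related | Yes | Yes | Yes |
| Grade 4, unrelated | No | Yes | No |

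Four cases agree and two differ.

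*Grade 4, unrelated.* Seriousness does not close this gap, because item 1 of the 10.4 list also requires at least possible relatedness. Item 4 closes it only where the physician believes the situation life threatening. A Grade 4 event under Table 1 of Section 10.1 (risk of death) would probably be caught that way. The cardiovascular grading table in the same section, however, allows Grade 4 hypertension on an indication for hospitalisation alone, as an alternative to life-threatening consequences. So the case can arise under the protocol's own grading.

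*Grade 3, related, one.* The synopsis and 10.4 require two such events and Section 13 gives no number. Section 13 uses the plural, so its count is open to argument.

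Two further differences sit alongside these. The synopsis stops dosing and notifies the SMC, whereas 10.4 pauses dosing and consults it. Within 10.4, the list places the grade criteria under serious events, but the lead sentence has no such limit.

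**Part 2: heart-rate stop.** Inputs: the printed formula (10.4) and the eligible ages of 18 to 65 (Section 6.2). The plan gives no worked value to reproduce.

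Printed stop = 220 − 0.85 × age:
- age 18: 220 − 15.3 = 204.7 bpm
- age 40: 220 − 34.0 = 186.0 bpm
- age 65: 220 − 55.25 = 164.75 bpm

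The maximal rate has to be assumed. The stop as a percentage of it is:

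| Assumed maximum | Age 18 | Age 40 | Age 65 | Label fits? |
|---|---|---|---|---|
| 220 − age | 204.7/202 = 101.3% | 186.0/180 = 103.3% | 164.75/155 = 106.3% | No |
| 210 − age | 204.7/192 = 106.6% | 186.0/170 = 109.4% | 164.75/145 = 113.6% | No |
| 230 − age | 204.7/212 = 96.6% | 186.0/190 = 97.9% | 164.75/165 = 99.8% | Yes |
| 220 − 0.7 × age | 204.7/207.4 = 98.7% | 186.0/192 = 96.9% | 164.75/174.5 = 94.4% | Yes |

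Under 220 − age the excess is 0.15 × age: 2.7, 6.0 and 9.75 bpm. With a slope of 1, the stop is at or above maximal for any intercept up to 220 + 0.15 × age, that is 222.7, 226.0 or 229.75 at the three ages. With the intercept at 220, it is at or above maximal for any slope of 0.85 or more.

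**The case against.** **The Grade 3/4 rules may be layered.** The synopsis and 10.4 act on dosing and Section 13 on enrolment, and a Section 13 hold could itself count as a pausing criterion. On that reading every section can be followed together. This stands as a possible reading, so a reader who infers that the sections cannot all be obeyed goes further than the text. But no section says that the Section 13 hold is included, and the linking sentence follows from the synopsis and 10.4 criteria, not from Section 13.

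**The link to enrolment is weak.** It speaks of a dosing cohort beside a next dosing level, while the design has one fixed regimen and defines no cohorts. Some 10.4 criteria, such as pregnancy, concern one participant, while Section 13 concerns the whole study. Both remarks are fair. They make the scope of 10.4 less clear, which is a further reason to state it.

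**The differing cases are few.** The grading table heads its Grade 4 column as potentially life-threatening, which moves such events towards item 4. What remains is an unrelated Grade 4 event that the physician does not believe life threatening, plus a single related Grade 3 event whose status depends on a plural. This stands and limits the size of the point.

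**The heart-rate rule is not contradicted inside the documents.** It gives one computable number for each age and is stated nowhere else. This also stands. A reader might infer that the brackets are misplaced, or that the threshold is shown to lie above maximal heart rate. Neither is supported: no maximal rate is defined, the label fits under two of the four assumptions tried, and the cited source is not available here.

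**Conclusion.** The point holds with limits and is a should-fix.

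**Grade 3/4 wording (main point; high confidence that it differs).** Unless the stopping or pausing criteria are taken to include the Section 13 hold, two of six cases receive different answers. The unrelated Grade 4 event outside item 4 is the firmer one; the single related, non-serious Grade 3 event rests on the natural reading of Section 13. The differences in action and in the place of seriousness are plain on the page.

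**Heart-rate stop (query; moderate confidence).** Label and formula disagree if maximal is 220 − age, and agree under other assumptions. It would be wrong to infer that participants are left unprotected. The 130 bpm hold, the blood-pressure holds and stops, suspension for a significant ECG abnormality, and the authority of the principal investigator and the SMC all remain. The condition for resuming after a hold is a minimum requirement, not an instruction to dose.

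No endpoint, analysis or sample size is affected.

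**What to change.** - Reconcile the synopsis (Planned Interim Analyses), Section 10.4 and Section 13. State the Grade 3 rule and the Grade 4 rule identically in each: number of events, relatedness, whether seriousness is required, the action, and whether it applies to dosing, to enrolment or to both.
- Say whether the stopping or pausing criteria in the linking sentence include the Section 13 hold, and define or remove the cohort wording on which that sentence depends.
- Check the heart-rate expression against the source that Section 10.4 cites, and make label and formula agree.

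The sponsor and the SMC set every threshold; none is proposed here. The cost is amendment wording only, with no extra participants, visits or procedures.
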